1. INTRODUCTION

The purpose of this SAP is to describe the planned analyses to be included in the Clinical Study Report (CSR) for Study 208022. Details of the planned interim analysis are also provided.

Additional exploratory analyses of inflammatory, metabolic and transcriptomic markers; data handling conventions and the specification of data displays will be provided in the Output and Programming Specification (OPS) document.

1.1. Changes to the Protocol Defined Statistical Analysis Plan

There are no changes to the originally planned statistical analysis specified in the protocol.

1.2. Objectives, Endpoints and Estimands

1.2.1. Objectives and Endpoints

Objectives	Endpoints
Primary	

 To determine the efficacy of GSK2982772 960 mg modified release (MR) once daily (QD) for 12 weeks, compared with placebo in participants with moderate to severe plaque psoriasis. 	
 PASI75 response (achieving $\geq 75\%$ improvement from Baseline in PASI score) at Week 12.
Secondary	

 To further evaluate the efficacy of GSK2982772 960 mg MR QD for 12 weeks, compared with placebo in participants with moderate to severe plaque psoriasis. 	
Further PASI parameters:
 
 PASI50, PASI90 and PASI100 response (achieving $\geq 50\%$, $\geq 90\%$ and 100% improvement from Baseline in PASI score, respectively) at Week 12. Change from Baseline PASI scores at Week 12. Static Investigator's Global Assessment (sIGA): sIGA response (achieving a sIGA score of CCI (0) or CCI (1)) at Week 12. 
Psoriasis Body Surface Area (BSA):
 
 Change from Baseline in psoriatic BSA at Week 12.
Safety	

 To evaluate the safety and tolerability of GSK2982772 960 mg MR QD for 12 weeks, compared with placebo in participants with moderate to severe plaque psoriasis. 	
 Adverse events Clinical laboratory values (clinical chemistry, haematology and urinalysis) Vital sign measurements (blood pressure, heart rate, respiratory rate and body temperature) 12-Lead electrocardiogram (ECG) monitoring Columbia Suicide Severity Rating Scale (C-SSRS)
Pharmacokinetics	

 To assess trough plasma concentrations of GSK2982772 960 mg MR QD for 12 weeks, in participants with moderate to severe plaque psoriasis. 	
 Trough plasma concentrations of GSK2982772 at Weeks 2, 4, 8, 12.
Exploratory	

 To investigate the efficacy of GSK2982772, 960 mg MR QD over time. 	Additional PASI parameters:

Objectives	Endpoints

compared with placebo in participants with moderate to severe plaque psoriasis.
	
 PASI75 response (achieving ≥75% improvement from Baseline in PASI score) at Weeks 2, 4, and 8. PASI50, PASI90 and PASI100 response (achieving ≥50%, ≥90% and 100% improvement from Baseline in PASI score respectively) at Weeks 2, 4, and 8. Change from Baseline PASI scores at Weeks 2, 4, 8. 
Static Investigator's Global Assessment (sIGA):
 
 sIGA response (achieving a sIGA score of CCI (0) or CCI (1)) at Weeks 2, 4, and 8. sIGA score category at Weeks 2, 4, 8, 12. 
Body Surface Area (BSA):
 
 Change from Baseline in BSA at Weeks 2, 4, and 8.

 To investigate effect of GSK2982772 960 mg MR QD for 12 weeks, on pathway and target engagement, transcriptomic profiling, inflammatory, and metabolic biomarkers in the skin and blood of participants with moderate to severe plaque-type psoriasis. 	
Pharmacology biomarker endpoints:
 
 Target Engagement Assay RIP1 (TEAR1) in blood at Weeks 0, 4, and 12. 
Transcriptomic profiling:
 
 Transcriptomic analysis, including but not limited to ribonucleic acid sequencing (RNA-seq), of messenger ribonucleic acid (mRNA) isolated from skin at Weeks 0, 4, and 12, with any changes in specific inflammatory gene transcript levels (e.g. IL-4, IL-10, IL-17, IL-21, IL-22, TNF and IFNγ) possibly being evaluated. 
Inflammatory and Keratinocyte biomarkers:
 
 Change from Baseline in histopathological scoring of psoriatic lesional biopsies, which may include, but are not limited to the following at Weeks 0, 4, and 12: epidermal thickness, keratin 16 (K16), antigen Ki-67 (Ki67), CD3, cluster of differentiation 11c (CD11c). Change from Baseline in inflammatory protein markers in blood which may include but are not limited to the following at Weeks 0, 4, and 12: IL-17, chemokine ligand 20 (CCL20), IL-6, IL-8, IL-4, C-X-C motif chemokine 10 (CXCL10). 
Metabolic biomarkers
 
 Change from Baseline in metabolic markers in fasting blood which may include but are not limited to the following at Weeks 0, 4, and 12:

Objectives	Endpoints
	homeostatic model assessment of insulin resistance (HOMA) (glucose and insulin), glycated hemoglobin (HbA1c), lipid panel.

Derivations of key primary and secondary endpoints (PASI, SIGA, BSA) will be given in the accompanying OPS document to this SAP. No rounding will be performed on PASI percentage change values when deriving PASI responder variables.

1.2.2. Estimands

Estimands were not incorporated into the protocol for this study. The missing data handling rules are outlined in analysis sections.

1.3. Study Design

Overview of Study Design and Key Features	
Design Features	
 Phase 1b/2a, multicentre, randomised, double-blind, placebo-controlled, parallel, repeat dose study of GSK2982772 in participants with active plaque-type moderate to severe psoriasis. The maximum total duration for each participant in the study will be 21 weeks: 
 Screening period of up to 35 days Treatment period of 12 weeks (84 days) Follow-up period for up to 28 days after last dose
Study intervention	
 Participants will receive either GSK2982772 960mg MR QD or placebo for 12 weeks (84 days). No dose modifications or adjustments are permitted per protocol.
Study intervention Assignment	
 Participants will be randomised to receive either GSK2982772 or placebo in a 2:1 ratio. Randomisation will be stratified by prior biologic use.
Interim Analysis	
 One interim analysis is planned to occur when at least six GSK2982772 participants complete the Week 12 visit or withdraw from study treatment.

2. STATISTICAL HYPOTHESES / SUCCESS CRITERIA

The primary objective of this study is to estimate the efficacy of GSK2982772 960 mg MR QD compared with placebo following 12 weeks of treatment, this will be assessed using the estimates of PASI75 response at Week 12.

There will be no adjustment for multiplicity.

3. SAMPLE SIZE DETERMINATION

Approximately 32 participants will be screened to achieve 21 participants randomly enrolled to either GSK2982772 or placebo in a 2:1 allocation ratio. Replacement participants may be randomised (up to approximately 6) into the study at the discretion of the Sponsor, to ensure that approximately 21 have completed the Week 4 visit.

The primary efficacy endpoint is PASI75 response (achieving $\geq 75\%$ improvement from Baseline in PASI score) at Week 12.

With a sample size of 21 participants there is approximately 99% probability of achieving a posterior probability of at least 97.5 that the true treatment difference over placebo is greater than zero. This is based on an assumed placebo response of 7%, an assumed true treatment difference of 55% and incorporating informative historical placebo data into the analysis. For the placebo arm an informative Beta (3.5, 46.5) distribution is assumed, with an effective sample size of 50 participants. For the active arm a vague Beta (1/3, 1/3) prior is used.

No sample size re-estimation is planned for this study.

4. ANALYSIS SETS

Analysis Set	Definition / Criteria	Analyses Evaluated
Screened	
 • All participants who were screened for eligibility 	
 • Study Population
Enrolled	
 • All participants who signed the ICF, passed screening and were eligible for randomisation (regardless of whether the participant went on to be randomised). • Note screening failures (who never passed screening even if rescreened) and participants screened but never enrolled into the study (Reserve, Not Used) are excluded from the Enrolled analysis set as they did not enter the study. 	
 • Study Population
Randomised	
 • All participants who were randomly assigned to study intervention in the study. • Participant must have signed ICF and passed Screening. 	
 • Study Population

Analysis Set	Definition / Criteria	Analyses Evaluated
	
 • Data will be reported according to the randomised study intervention. 	
Intent to Treat (ITT)	
 • All participants who were randomised to study intervention in the study and who received at least one dose of study intervention. • Data will be reported according to the randomised study intervention. 	
 • Efficacy
Modified Intent to Treat (ITT)	
 • All participants in the ITT population who completed at least the Week 4 assessment. • Data will be reported according to the randomised study intervention. 	
 • Efficacy
Safety	
 • All participants in the enrolled population who received at least one dose of study intervention. • Data will be reported according to the actual study intervention received. 	
 • Safety • PD
COVID-19	
 • All participants in the Safety set who had a confirmed, probable or suspected COVID-19 case diagnosis. 	
 • COVID outputs
Pharmacokinetic (PK)	
 • All participants in the Safety population who had at least one non-missing PK assessment (Non-quantifiable [NQ] values will be considered as non-missing values). • Data will be reported according to the actual study intervention received. 	
 • PK

Actual treatments are defined as follows: If a participant randomised to the placebo arm receives any amount of GSK2982772 he or she will be included in the corresponding active treatment arm.

4.1. Protocol Deviations

Important protocol deviations (including deviations related to study inclusion/exclusion criteria, conduct of the trial, patient management or patient assessment) will be summarised.

Protocol deviations will be tracked by the study team throughout the conduct of the study. These protocol deviations will be reviewed to identify those considered as important as follows:

- Data will be reviewed prior to unblinding and freezing the database to ensure all important deviations are captured and categorised in the protocol deviations system independent dataset (DV1).
- This dataset will be the basis for the summaries of important protocol deviations.

Data will be reviewed prior to unblinding and freezing the database to ensure all deviations are captured and categorised in the protocol deviations A&R dataset.

4.1.1. Definitions for Per Protocol Analysis Set

This study will not include a Per Protocol analysis set.

5. STATISTICAL ANALYSES

5.1. General Considerations

Unless otherwise specified, the Enrolled or Randomised Analysis Sets will be used for all Study Population analyses (detailed in the OPS), the Intent to Treat Set will be used for all Efficacy analyses, PK Set will be used for PK analyses and Safety Analysis Set will be used for all safety and PD analyses, COVID specific outputs as well as a subset of safety analyses will be produced using the COVID population.

In the case of wrong stratification assigned at the time of randomization, the analyses will be performed based on the data collected in the electronic case record form (eCRF), not the assigned stratum at randomization.

Credible intervals (CrI) will be equal-tailed and use 95% level unless otherwise specified.

Unless otherwise specified, summary tables will provide the following descriptive statistics as a minimum:

- Continuous data (normally distributed):
n, mean, standard deviation (SD), median, minimum and maximum.
- Continuous data (log-normally distributed):
n, geometric mean, SD on the log scale (SD (log)), median, minimum and maximum.
- Categorical data:
number and percentage of participants in each category.

Figures of average responses to primary and secondary endpoints for each treatment group over time will be produced including a suitable measure of uncertainty. Adjusted (posterior) values will be used where available.

5.1.1. Bayesian Analysis

The analyses will be conducted in the Bayesian framework. Models will be fitted by MCMC simulations and informative priors may be used. In that case, a sensitivity analysis using vague priors will also be carried out. Prior distributions are given in the analysis sections below and will be reported in the CSR. Posterior values will be calculated by weighting categorical coefficients level according to the proportions observed in the data and taking the mean value of continuous covariates.

For continuous endpoints, posterior distributions for each arm will be summarized using: posterior mean, SD, 95% CrI, as well as posterior mean and 95% CrI for the difference between arms. Medians may be used in place of medians for skewed posterior distributions.

For categorical endpoints, posterior distributions for each arm will be summarized using: posterior median response rate and 95% CrI, as well as posterior median difference in response rates and odds ratios and associated 95% CrIs.

Posterior probabilities of being greater than thresholds of interest may also be presented.

Any additional requirements for a particular analysis are given alongside the analysis description.

Bayesian Model Checking & Diagnostics

• A minimum burn-in period of 5,000 MCMC samples will be used.• A minimum of 10,000 MCMC samples will be run to generate samples of the posterior distribution.• Convergence will be assessed using visual inspection of trace plots and autocorrelation plots, the ratio of the Monte Carlo Standard Error (MCSE) to the SD of the posterior distribution (ratio should be <0.01).• If the model is not deemed to have converged the following actions will be taken in the order described below:
○ Increasing the number of MCMC samples and/or the thinning will be explored. The blocking of the parameters will be considered.

5.1.2. Baseline Definition

Baseline value will be the latest pre-dose assessment with a non-missing value, including those from unscheduled visits. If time is not collected, Day 1 assessments are assumed to be taken prior to first dose and will be used as baseline.

Screening values may be used if Day 1 data is unavailable for efficacy and safety endpoints. Otherwise, if not Screening data available, baseline will be set to missing.

5.1.3. Multicenter Studies

Due to the small sample size, the number of participants per site will be small. It is anticipated that analyses by centre would unlikely be informative and will not, therefore, be provided.

5.2. Primary Endpoint(s) Analyses

5.2.1. Definition of endpoint(s)

The primary endpoint for this study:

- PASI75 response at Week 12 (Day 85), where PASI75 response is defined as a reduction in PASI score from baseline of at least 75%.

5.2.2. Main analytical approach

The primary analysis will be produced for the ITT population.

The summary measure of interest is the difference in PASI75 response rates at Week 12 (Day 85) between GSK2982772 and placebo. Missing values will be imputed as non-responders.

The primary endpoint will be analysed using a Bayesian logistic regression model, details given in [Table 2](#). Summary statistics will be provided for the posterior distribution of the true difference in PASI75 response rate (GSK2982772 vs placebo) as well as posterior probabilities for a range of thresholds.

A non-informative prior will be used for the PASI75 response rate on GSK2982772 and covariates.

An informative prior will be used for the placebo response rate of the form: 90% weight on $Be(5.39, 69)$ and 10% on $Be(1/3, 1/3)$. The prior was derived from historical data from similar clinical trials using meta-analytic predictive prior (MAP) approach, the effective sample size is approximately 63 [[Schmidli, 2014](#)].

In the event that the placebo prior is different from what is presented here, this will be documented in the CSR.

Table 2 Statistical Analysis of Primary Endpoint

Endpoint(s)	

 PASI75 response at Week 12 (Day 85) 	
Analysis Method	
Bayesian Logistic Regression (using informative prior)	
Model Specification	
Outcome	$y_i = \text{Response (0/1) for participant } i$
Predictors	
 Treatment (categorical) Prior Biologic Use (categorical) Baseline PASI score (continuous) 
Unless stated otherwise the predictors (not including study treatment) will be centered around their estimated mean prior to inclusion in the model

Model	$y_i \sim \text{Ber}(p_i)$ $\text{logit}(p_i) = (\text{Treatment=Placebo}) \times \beta_1 + (\text{Treatment=GSK}) \times \beta_2 + (\text{Prior Biologic Use}^*) \times \beta_4 + (\text{Baseline PASI score}^*) \times \beta_5$
Prior distributions for coefficients (β)	β = fixed effect parameters associated to predictors 
 β_1: informative prior such that $\text{logit}^{-1}(\beta_1) \sim$ mixture of Betas* β_2: non-informative prior such that $\text{logit}^{-1}(\beta_2) \sim \text{Beta}(1/3, 1/3)$ Other β_k: non-informative priors of $N(0, SD=100)$ 
*Expected prior is a mixture of $Be(5.39, 69)$ and $Be(1/3, 1/3)$, weighted to 90% and 10% respectively. Final prior will be reported in the CSR.

Model Checking & Diagnostics	
See Section 5.1.1	
Results Presentation	

 Posterior medians and 95% CrI of true response rate for each treatment group. Posterior medians and 95% CrI for the true difference in proportion of responders (GSK2982772 – placebo) and odds ratios of GSK2982772 to placebo. Probabilities that the true treatment difference is greater than a range of values of interest (e.g. 0%, 20%, 45%, 55%). See OPS outputs list for details. Probabilities that the true response rate on active is greater than a range of values of interest (e.g. 0%, 30%, 55%). See OPS outputs list for details. 	
Interim Analysis	

The interim analysis will estimate the predictive probability of meeting various decision criteria including:
 
 >55% probability that true difference in PASI75 response (GSK2982772 – Placebo) above 45% >97.5% probability that true difference in PASI75 response (GSK2982772 – Placebo) above 0% 	

Predictive probabilities will be calculated via simulation assuming a total sample size of 21 (14:7 for GSK2982772:Placebo).

The parameter posterior distributions from the Bayesian logistic regression analysis of interim data will be used to simulate predicted PASI75 responses for remaining trial subjects. For participants yet to be enrolled, average covariate values will be assumed.

The predicted data will be combined with the observed interim data and the Bayesian logistic model applied to assess the decision criteria. This process will be repeated for each run of the MCMC procedure. The proportion of times the decision criteria is met will be the predicted probability.

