6.2. Measures to Minimize Bias: Randomisation and Blinding

Randomisation

At Screening, a unique Participant Number will be assigned to any participant who has at least one Screening procedure performed, other than informed consent. The unique Participant Number will be used to identify individual participants during the course of the study.

Participants who meet Screening eligibility criteria will be randomised to a treatment group through an Interactive Web Response System (IWRS). Before the study is initiated, the log in information & directions for the IWRS will be provided to each site. The IWRS will confirm the participant's case report form (CRF) number (Participant Number) and provide the randomisation number, where:

• A randomisation number will be assigned from a randomisation schedule generated by Clinical Statistics, prior to the start of the study, using validated internal software.

Once assigned, this number must not be reassigned to any other participant in the study. The randomisation is centrally controlled by the IWRS.

Participants will be randomised to receive either GSK2982772 or placebo in a 2:1 ratio. The randomisation will be stratified by prior biologic use. Participants will take study medication every day, once a day for 12 weeks, at approximately the same time each day.

Participants will be administered the first daily dose of study medication by site staff during the site visit for Day 1 (Week 0). At subsequent visits, the dose should be taken either on site (preferred) after the pre-dose assessments, or after the visit at home only if the participant dosing at site would result in a treatment overdose (refer to Section 8.4). Participants will self-administer all other doses of study medication and will record the date and time in the diary cards provided to them. Returned study intervention should not be re-dispensed to the participants.

See the SRM for further details.

Blinding

This will be a double-blind study.

Access to participant-level unblinded data will be restricted to the GSK Biostatistics and CPMS members of the study team for the purpose of conducting analyses for the planned interim analysis. Summary-level data will be shared with the internal DRC at the interim analysis, membership of which will be listed in a data review charter. Results of the interim will not be shared outside of this committee, only the decision and its

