9.4. Statistical Analyses

The statistical analysis plan (SAP) will be finalized prior to the first unblinded data look (interim analysis) and it will include a more technical and detailed description of the statistical analyses described in this section. This section is a summary of the planned statistical analyses of the most important endpoints including primary and key secondary endpoints.

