9.4.1. Primary Analyses

Efficacy analyses will be based on the ITT population unless stated otherwise in the SAP. The primary analysis will assess the difference in PASI75 response rates between GSK2982772 960 mg and placebo at Week 12. A Bayesian logistic regression analysis of the difference in PASI75 response rates at Week 12 will be conducted to calculate posterior probabilities that the true effect of GSK2982772 relative to placebo is greater than a range values of interest.

An informative prior will be used for the placebo arm to leverage relevant historical placebo data into the analysis. It is expected that this prior will be a Beta (3.5, 46.5)

distribution, giving the historical data an effective sample size of 50 participants. Further emerging placebo data may be incorporated into the prior distribution for the placebo arm prior to breaking the study blind. A non-informative prior will be used for the PASI75 response rate on GSK2982772.

Participants who discontinue early or have missing PASI data at any visit will be treated as PASI75 non-responders at that time point (regardless of their response at previous visits). Sensitivity analyses will be conducted to investigate the impact of this approach to handling missing data.

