9.5. Interim Analyses

An interim analysis is planned to occur when at least six participants on GSK2982772 have completed the Week 12 visit or discontinued study treatment to aid internal decision making around subsequent GSK2982772 trials. The study may be stopped for futility if the probability of a positive outcome at the end of the trial is low based on the data available at the interim. There is no plan to stop the trial early based on positive efficacy data.

The data will be reviewed by an internal DRC. The committee will include the study statistician, the study pharmacokineticist and a limited number of GSK individuals. The charter will identify the specific individuals to form part of the DRC, as well as detail the data to be reviewed, planned analyses, guidelines for the decision rules to be followed and a dissemination plan for interim decisions.

The interim will focus on efficacy data including, but not limited to, PASI response rates and change in PASI score from Baseline.

The SAP and data review charter will describe the planned interim analyses in greater detail.

Safety monitoring of blinded data will be conducted by the internal GSK Safety Review Team (SRT) at regular intervals throughout the study, see Section 8.2.

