5.8. Interim Analyses

An interim analysis (IA) is planned to occur when at least six participants on GSK2982772 have completed the Week 12 (Day 85) visit or withdrawn from study treatment. The purpose of the IA is for internal decision making about future GSK2982772 trials and assess futility. The study may be stopped for futility if the probability of a positive outcome at the end of the trial is low based on the data available at the IA. The trial cannot be stopped early based on positive efficacy data.

Predictive probabilities will be calculated via simulation. The parameter posterior distributions from the Bayesian logistic regression analysis of interim data will be used to repeatedly simulate PASI75 response for remaining trial subjects. The predicted data will be combined with interim data to assess end of study criteria and calculate the proportion of times the decision criteria are met.

The data will be reviewed by an internal Data Review Committee. The committee will include the study statistician, the study pharmacokineticist and a limited number of GSK staff. A DRC charter will identify the specific staff to form part of the DRC, as well as detail the data to be reviewed, planned analyses, guidelines for the decision rules to be followed and a dissemination plan for interim decisions.

A subset of the outputs for the end of study will be produced for the IA. These will focus on efficacy data including, but not limited to:

- Summaries of PASI response data and change from baseline in PASI score by treatment and visit as outlined in Section [5.3.2](#) (Modified ITT population).
- Bayesian analysis of PASI75 response at Week 12 (Day 85) as outlined in Section [5.2.2](#) (Modified ITT population).
- Summaries of PK data and predicted target engagement as outlined in Section [5.5](#) (PK population).
- Summary of longitudinal model used to predict PASI score and the derived PASI75 at Week 16, outlined in Section [5.5.1](#), (conducted by CPMS on the ITT population).
- Summaries of disposition and psoriatic baseline characteristics (Randomised population).

Safety monitoring of blinded data will be conducted by the internal GSK Safety Review Team (SRT) at regular intervals throughout the study, see Section 8.2 of Protocol.

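### Could the primary placebo prior be changed after the interim look, because SAP 5.2.2 asks only that a different prior be reported in the CSR?

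*SAP*

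**What the plan says.** **Protocol 9.4.1** expects a Beta(3.5, 46.5) placebo prior and permits one kind of change: "Further emerging placebo data may be incorporated into the prior distribution for the placebo arm prior to breaking the study blind".

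**SAP 5.2.2** replaces that prior with a robust mixture, 90% Be(5.39, 69) and 10% Be(1/3, 1/3). The SAP version history logs a clarification of the placebo prior. The text then says: "In the event that the placebo prior is different from what is presented here, this will be documented in the CSR". Table 2 describes the mixture as the expected prior and adds: "Final prior will be reported in the CSR". Neither sentence repeats the protocol's time limit.

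**SAP 1.1** states: "There are no changes to the originally planned statistical analysis specified in the protocol".

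**Protocol 9.4** states: "The statistical analysis plan (SAP) will be finalized prior to the first unblinded data look (interim analysis").

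**Interim access.** Protocol 6.2 says "Access to participant-level unblinded data will be restricted to the GSK Biostatistics and CPMS members of the study team", and the same sentence limits the purpose to running the planned interim analyses. On the data review committee, protocol 9.5 says: "The committee will include the study statistician, the study pharmacokineticist and a limited number of GSK individuals". SAP 5.8 lists among the interim outputs the "Bayesian analysis of PASI75 response at Week 12 (Day 85) as outlined in Section" 5.2.2, so the primary model is run on interim data.

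**The concern.** The primary estimate rests on the placebo prior plus about 7 concurrent placebo participants, so the prior supplies most of the placebo information. It should be fixed without sight of the trial's own placebo responses.

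The SAP wording is looser than the protocol's in two ways. It names no date, and it covers any different prior (another mixture weight, for example), not only added placebo data. Neither document says whether breaking the study blind means the interim or the final unblinding. The people able to revise the prior overlap with those who see unblinded interim data.

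If a revision after the interim were open, a reader of the CSR would learn that the prior had changed, but not whether the trial's own placebo outcomes had influenced the choice.

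**Working it through.** **1. The passages together**

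| Question | Text | What it settles |
|---|---|---|
| What may change? | Protocol 9.4.1 | Added placebo data only |
| Until when? | Protocol 9.4.1 | Before the blind is broken |
| When is the first unblinded look? | Protocol 9.4 | The interim; the SAP is to be final by then |
| Does the SAP depart from this? | SAP 1.1 | It declares no departure |
| What does SAP 5.2.2 add? | Disclosure sentences | A different prior is reported in the CSR |

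A duty to report a different prior does not create a new right to choose one. With no departure declared, the protocol limit still governs, and its natural date is the interim.

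**2. Reproducing the planning figure**

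Inputs: 14 active and 7 placebo participants (SAP Table 2, interim part); rates of 62% (7% + 55%) and 7%, and active prior Beta(1/3, 1/3) (protocol 9.2). Covariates are ignored.

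For x active and y placebo responders:

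- Active posterior: Beta(1/3 + x, 1/3 + 14 − x).
- Placebo posterior: each component Beta(a, b) becomes Beta(a + y, b + 7 − y), with weight proportional to prior weight × B(a + y, b + 7 − y) / B(a, b).
- Pr(difference > 0) is obtained by numerical integration. The binomial probabilities of all (x, y) with Pr > 0.975 are then summed.

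| Placebo prior | Chance of Pr(diff > 0) > 97.5% at 62% vs 7% |
|---|---|
| Beta(3.5, 46.5), protocol | 99.7% (protocol states about 99%) |
| SAP mixture | 98.1% |
| Beta(1/3, 1/3), vague | 84.3% |

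**3. The change the protocol allows**

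Add n historical placebo participants responding at rate r, so the informative component becomes Beta(5.39 + nr, 69 + n(1 − r)), and keep the 90:10 weights. The values of n and r are assumptions, because the documents give none. Entries are the share of trials that fall on the other side of 97.5% than under the SAP mixture, for n = 50 / 100 / 200.

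| r | True rates 62% vs 7% | True rates 62% vs 15% (assumed) |
|---|---|---|
| 4% | 0 / 0.2 / 1.2% | 0 / 0.7 / 3.6% |
| 7% | 0 / 0 / 0% | 0 / 0 / 0% |
| 10% | 0.8 / 0.8 / 0.8% | 1.9 / 1.9 / 1.9% |

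**4. What the interim could reveal**

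The trigger is six active participants. At 2:1 that implies about 6 / 2 = 3 placebo participants. The chance of at least one placebo responder among them at a 7% rate is 1 − 0.93³ = 19.6%. In about four of five such interims, the placebo data would give no reason to revisit the prior.

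**The case for a change.** The best case for a change is that the protocol does not settle the date. Protocol 6.2 keeps the rest of the study team blinded throughout, and SAP 4.1 mentions unblinding alongside the database freeze, so a final-unblinding reading is possible. A SAP finalised before the interim does not fix the prior if that SAP itself leaves the prior open. Disclosure shows that a change occurred, not that it was made blind. The mixture weight, which only the SAP wording leaves free, matters more than added data: with the robust weight at 50% instead of 10%, 5.3% of trials cross the 97.5% line at 62% vs 7%, and about 14% at 62% vs 15%.

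Part of this stands. The lock date is not written down, and Table 2 does call the prior expected. The larger figures carry little weight, however. No passage mentions a 50% weight, the 14% also needs an assumed placebo rate about twice the planned one, and changing the weight lies outside what protocol 9.4.1 permits. Nothing in the documents suggests a change after the interim. The logged move from Beta(3.5, 46.5) to the mixture was towards the stricter prior (98.1% against 99.7%).

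Nor would an explicit lock be free. It would choose between two readings of a protocol phrase, so it would need a protocol clarification or a declared change in SAP 1.1. It would also shut out of the primary analysis any relevant placebo data that emerge after the interim.

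**Conclusion.** No change is needed. The SAP omits a detail that a statistician following both documents would supply correctly: the prior is settled before the interim, and the CSR reports it.

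The effect of the permitted kind of change is 0 to 1.2% of trials crossing the 97.5% line at the planning rates, and 0 to 3.6% at an assumed 15% placebo rate. These figures rest on a 14:7 split, no covariates, and assumed sizes and response rates for the added data. The line itself is not a success rule: SAP section 2 frames the study as estimation, and the threshold serves as one of the criteria for predictive probabilities at the interim.

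Safeguards are already in place. SAP 5.2.3 commits to a vague-prior analysis, the final prior is to be disclosed, and there is no stop for positive efficacy. The committee charter and the Output and Programming Specification were not available and may already record a lock date.
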